10.6. Study Drug Accountability

The Investigator is responsible for confirming that all study drug supplies received by the study site are inventoried and accounted for throughout the study. A drug receipt log will be completed and signed by the person accepting the shipment. It is important that the designated study site personnel count and verify that the shipment contains all the items noted in the shipment inventory. Any damaged study drug found in a given shipment will be documented in the study files. The Investigator must notify the SKLSI of any damaged or unusable study drug supplies.

10.7. Study Drug Handling and Disposal

Upon destruction of study drug, a Certificate of Destruction (COD) will be provided to SKLSI. See the Pharmacy Manual for drug handling and disposal. The clinical site will be responsible for cenobamate drug disposal.

11. PHARMACOKINETIC ASSESSMENTS

11.1. Blood Sample Collection

Blood samples for determination of cenobamate plasma concentrations will be collected by direct venipuncture into a labeled tube containing the appropriate anticoagulant as specified by the bioanalytical facilities. If judged necessary by the clinical staff, blood samples may be collected from an indwelling cannula (catheter).

The complete schedule for pharmacokinetic blood sampling is presented in [Table 4](#). The time of blood sample collection will be calculated according to the treatment administration schedule. The clock time of the dose administration will be recorded (record time after all drug products have been swallowed). The exact actual time of blood draws will be recorded and reported for all subjects in the CRF. Actual blood collection times will be used for the PK analysis. Blood will be collected into tubes labeled with the nominal blood sampling times.

It is important to avoid hemolysis during blood collection. In case of hemolysis, this will be reported in the CRF. The impact of any observed hemolysis on the plasma concentrations may be discussed with SKLSI.

When a sampling time is close to a mealtime, the sample will be collected before the meal.

Blood samples for PK analysis should be collected at the requested times, but the allowed windows for sample collection are presented in [Table 6](#).

Table 6: Acceptable Time Windows for PK Blood Sampling

Nominal Sampling Time	Acceptable Time Windows
Pre-dose	-30 mins before dose or immediately before dosing
0.25 to 1.5 hour post-dose	± 2 minutes
2 to 12 hours post-dose	± 5 minutes
14 to 96 hours post-dose	± 15 minutes
120 to 456 hours post-dose	± 2 hours
Follow-up	± 1 day

The approximate blood volume to be collected per subject following a single oral dose of cenobamate (tablet or suspension) is presented in [Table 7](#).

Table 7: Blood Volume to be Collected per Subject for Drug Plasma Concentration Analysis After a Single Dose of Cenobamate (456 Hours)

Formulation (Fed Status)	Number of Timepoints	Volume per Timepoint (mL)	Total Volume (mL)
Cenobamate Oral Tablet (Fasted)	24	2	48
Cenobamate Oral Suspension (Fasted)	24	2	48
Cenobamate Oral Suspension (Fed)	24	2	48
Total	72	6	144

11.2. Urine Sample Collection

Urine will not be collected for PK assessment in this Study.

11.3. Sample Analysis

11.3.1. Sample Processing and Handling for PK Assessment

Detailed procedures for the sample collection, processing and handling for PK assessment will be provided in a separate document (i.e., Laboratory Manual). The shipment address and assay lab contact information will be provided to the investigational site prior to initiation of the trial.

11.3.2. Bioanalysis

Blood samples will be processed, split, stored, and shipped according to the sample processing manuals supplied by the bioanalytical facilities.

Plasma samples will be analyzed for cenobamate concentrations using a validated liquid chromatography/tandem mass spectrometry method (LC-MS/MS) with a lower limit of quantification of 0.05 µg/mL.

The method, data acceptance criteria, and criteria for sample re-assay will follow the bioanalytical facility's SOPs and the guidelines set by the Regulatory Agencies.

Pharmacokinetic sample analysis methods are further explained in Section 13.1.3.

PK blood samples may be used for metabolite or methodology exploratory analyses. Possible results from these exploratory analyses may be reported in standalone report(s) if deemed necessary.

11.3.3. Exploratory Pharmacogenomic Assessments

At the time point defined in the Schedule of Assessments (Table 4), an optional blood sample will be collected to explore the possible effect of genetic variation in the PK of cenobamate. A separate informed consent for genotyping will be obtained from each subject prior to sampling. DNA will be extracted from the blood sample in order to sequence genes coding for enzymatic or transporter systems that are involved in the absorption, distribution, metabolism and excretion (ADME) of drugs. The gene sequences to be determined include known and likely functional variations of key ADME genes and incorporate more than 90% of ADME-related genetic markers identified by the PharmaADME group (weblink.pharmaadme.org). It is not intended to include the pharmacogenomic data in the final CSR. However, this may be considered if deemed necessary. Possible results from these exploratory analyses may be reported in standalone report(s) if deemed necessary.

12. ASSESSMENT OF SAFETY

12.1. Safety Parameters

Safety assessments will include physical examination, vital signs, safety laboratory tests, continuous AE monitoring, C-SSRS review and concomitant medication recording. Additional safety measurements may be performed at the discretion of the Investigator for reasons related to subject safety.

Clinically significant physical examination findings prior to the first dose of the study treatment will be recorded as part of the medical history. Clinically significant findings after the first dose will be recorded as AEs.

The procedures and associated collection windows for vital signs will be as follows:

- On days that drug product is administered, within 2 hours for pre-dose assessments (Days 1, 22, and 43).
- \pm 10 minutes for post-dose assessments (Days 4, 6, 9, 12, 16, 20, 25, 27, 30, 33, 37, 41, 46, 48, 51, 54, 58, 62 and 69).

Unless otherwise stated in this protocol, the clinical site's standard operating procedures (SOPs), which are available for all activities relevant to the quality of the study, will be followed during this study.

The study procedures to be conducted for each subject in the study are detailed in [Table 4](#).

The order of the assessments when scheduled at the same theoretical time will be as follows:

1. Vital signs;
2. PK blood sampling;
3. Blood and urine sampling for safety laboratory assays;
4. Symptom oriented physical examination.

Any deviation from the protocol procedures will be captured in the protocol deviation tracker and filed in the Transfer Master File (TMF).

12.1.1. Adverse Events

All AEs which occur during the clinical study will be reported in detail in the source documents and documented in the eCRF from Screening, throughout the clinical conduct until the final follow-up visit. SAEs will be continuously monitored starting after the time of informed consent through the follow-up visit. The Investigator should follow all unresolved AEs until the events have resolved or have stabilized, the subject is lost to follow-up, or it has been determined that the AE is not related to study drug or study participation. Outcome of AEs (and resolution date, if applicable) should be documented on the appropriate eCRF page(s) and in the subject's medical record.

Detailed information about intensity, relationship to study drug, expectedness, seriousness criteria, follow-up and reporting of AEs and SAEs are provided in the further sections ([Section 12.2](#) to [Section 12.5](#)).

Special attention must be given to findings and symptoms related to rash and/or hypersensitivity that might be linked to DRESS (Drug Rash with Eosinophilia and Systemic Symptoms) syndrome. For details, see Section [12.5.3](#)).

Pregnancy of female subjects and female partners of male subjects will be monitored along with follow-up, if warranted (see Section [12.1.7.7](#)).

12.1.2. Demographic/Medical History

The medical history will include evaluation at Screening of ears, nose, and throat, and will comprise any ophthalmological, cardiovascular, respiratory, musculoskeletal, gastrointestinal, genitourinary, neurological, endocrine, psychiatric, immunological or allergic, dermatological, and hematological disease, and family history disorder. All findings on medical history will be evaluated by the Investigator for clinical significance.

12.1.3. Vital Signs

Vital sign measurements (oral body temperature, pulse rate, respiratory rate and blood pressure) are specified in [Table 4](#).

Blood pressure, pulse rate, and respiratory rate will be measured after being in supine position for at least 5 minutes. The allowable time frame for collecting pre-dose vital signs is within 2 hours prior to dosing.

Vital signs can also be monitored at any time during the study when judged necessary by the Investigator.

12.1.4. Suicidality Assessment

The Columbia Suicide Severity Rating Scale (C-SSRS) is a brief questionnaire that provides for the identification, quantification, and standardized assessment of the occurrences and severity of suicidal ideation and behavior. The “Baseline/Screening Version” of the C-SSRS will be assessed at Screening. The C-SSRS “Since Last Visit” version will be assessed on Day -1,20, 41 and 69, as specified in [Table 4](#) of the Schedule Of Assessments.

12.1.5. Weight and Height

Height will only be recorded at the Screening visit. Weight will be measured, and BMI will be calculated at time points indicated in the Schedule of Assessments ([Table 4](#)).

12.1.6. Physical Examination

A complete physical examination consisting of a review of all body systems and a symptom-directed physical examination will be performed at time points indicated in the Schedule of Assessments ([Table 4](#)). A symptom-directed physical examination may be conducted at any time per Investigator’s discretion.

Demographic data (date of birth, gender, race, and ethnicity), and alcohol and smoking habits will be recorded in the site’s source document at the Screening Visit.

12.1.7. Electrocardiogram (ECG)

ECG will be collected at screening and baseline only. A subject must be in the supine position for at least 10 mins prior to any ECG reading. An ECG may be repeated if necessary

12.1.8. Laboratory Assessments

The tests listed in [Table 8](#) will be performed by the local laboratories at time points indicated in the Schedule of Assessments ([Table 4](#)).

Table 8: Clinical Laboratory Tests

Hematology and Coagulation	Serum Chemistry	Urinalysis	Additional Tests
Hemoglobin	Sodium	pH	
Hematocrit	Potassium	Specific gravity	Serology: anti-HIV-1/2, HBsAg, anti-HCV
Erythrocytes	Chloride	Color	
Platelets	Calcium	Protein	FSH test
Leukocytes	Inorganic phosphate	Glucose	for postmenopausal women, including women whose last menstruation was < 1 year before screening
Neutrophils	Urea	Ketones	
Eosinophils	Creatinine	Hemoglobin (erythrocytes)	
Lymphocytes	Uric acid		
Monocytes	Total bilirubin	Leukocytes	Serum pregnancy test for women of childbearing potential, including women whose last menstruation was < 1 year before screening
Basophils	Direct bilirubin	Microscopic analysis, if urine is positive for protein, leukocytes or hemoglobin	
INR	ALT		
aPTT	AST		
PT	GGT		
	AP		
	LDH		Urine drugs of abuse test including but not limited to cannabinoids, amphetamines, methamphetamines, opiates, methadone, cocaine, benzodiazepines, and barbiturates
	CPK		
	Amylase		
	Lipase		
	Triglycerides		
	Total cholesterol		
	HDL cholesterol		
	LDL cholesterol		
	Total protein		
	Albumin		
	Glucose		Alcohol breath test

INR: International Normalized Ratio; aPTT: Activated Partial Thromboplastin Time; PT: Prothrombin Time; ALT: Alanine Aminotransferase; AST: Aspartate Aminotransferase; GGT: Gamma-glutamyl Transferase; AP: Alkaline Phosphatase; LDH: Lactate Dehydrogenase; CPK: Creatine Phosphokinase; HDL: High Density Lipoprotein; LDL:

Low Density Lipoprotein; HIV: Human Immunodeficiency Virus; HBsAg: Hepatitis B Surface Antigen; HCV: Hepatitis C virus.

The clinical laboratory will clearly mark all laboratory test values that are outside the normal range and the Investigator will indicate the clinical significance according to the applicable clinical site's Standard Operating Procedure (SOP). Detailed information about follow-up of abnormal laboratory results is given in Section 12.5.1. The procedures for the collection, handling, and shipping of laboratory samples are specified in the laboratory manual(s) provided to the clinical site.

Table 9 lists the blood volume to be collected throughout the course of the study per subject. The projected total blood volume to be collected during this study is 397.7 mL. For comparison, a blood donation is generally about 450 mL.

Table 9: Blood Volume to be Withdrawn During the Conduct of the Study

Blood Draw Reason	N	Volume (mL)	Total (mL)
Pharmacogenomic Sampling	1	6	6
Hematology	12	2	24
Clinical Chemistry at Screening (includes FSH, pregnancy, lipid panel, serology)	1	17	17
Clinical Laboratory Tests (During Study)	12	5	60
Coagulation Lab Tests (Screening)	1	2.7	2.7
PK Blood Sampling	72	4	288
		TOTAL	397.7

12.1.8.1. Hematology

Please refer to [Table 8](#) for hematological assessments to be collected throughout the study at times specified in [Table 4](#).

12.1.8.2. Blood Chemistry

Please refer to [Table 8](#) for serum chemistry assessments to be collected throughout the study at times specified in [Table 4](#).

12.1.8.3. Urinalysis

Please refer to [Table 8](#) for urinalysis assessments to be collected throughout the study at times specified in [Table 4](#).

12.1.8.4. Virus Serology

Please refer to [Table 8](#) for viral serology tests to be collected throughout the study at times specified in [Table 4](#).

12.1.8.5. Drug Screen

Please refer to [Table 8](#) for drugs that will be screened for at times specified in [Table 4](#).

12.1.8.6. Additional Tests

Please refer to [Table 8](#) for any assessments to be collected throughout the study at times specified in [Table 4](#).

12.1.8.7. Pregnancy

Please refer to [Table 8](#) for pregnancy tests to be collected throughout the study at times specified in [Table 4](#).

Pregnancy in a female subject in the study shall be reported to the Medical Monitor, SK Life Science, Inc. (SKLSI), and IQVIA on the Pregnancy Reporting Form, faxing and emailing the form as per the Table of Contact ([Table 12](#) to [Table 14](#)), within 24 hours of the knowledge of its occurrence by the Investigator or designee (for pregnancies occurring during the course of the study or immediately following the end of the study). Pregnancy in itself is not regarded as an AE, unless there is a suspicion that an investigational product may have interfered with the effectiveness of a contraceptive medication. The Investigator must discuss with the medical monitor/Sponsor, in conjunction with the Institutional Board (IRB), whether or not it would be appropriate for the subject to continue in the study. Because of the possibility that the fetus/embryo could have been exposed to the investigational product through the parent and for the subject's safety, the pregnancy will be followed up to determine its outcome, including spontaneous or voluntary termination, details of birth, presence or absence of any birth defects, congenital anomalies, or maternal and/or newborn complications. Pregnancy complications and elective terminations for medical reasons should not be reported as an AE or SAE. All reports of congenital abnormalities/birth defects are SAEs. Spontaneous miscarriages should also be reported and handled as SAEs.

The pregnancy will be recorded on a Pregnancy Form and reported by the Investigator or designee to the Sponsor. Pregnancy follow-up will also be properly recorded to ensure quality and completeness of the data belonging to the investigational product and will include an assessment of the possible causal relation between the investigational product and any pregnancy outcome.

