12.2.1.2. Serious Adverse Event (SAE)

An **SAE** or reaction is any untoward medical occurrence that at any dose:

- Results in death,
- Is life-threatening,
- Requires nonscheduled (not routine or planned) subject hospitalization for ≥ 24 hours or prolongation of existing hospitalization for ≥ 24 hours,
- Results in persistent or significant disability or incapacity (defined as a substantial disruption of a person’s ability to conduct normal life functions),
- Is a congenital anomaly or birth defect,
- Is an important medical event defined as an event that does not fit one of the other outcomes but may jeopardize the subject and may require medical or surgical intervention (treatment) to prevent one of the other outcomes. Examples include allergic bronchospasm (a serious problem with breathing) requiring treatment in an

emergency room, serious blood dyscrasias (blood disorders), or seizure/convulsion that does not result in hospitalization. The development of drug dependence or drug abuse would be other examples of important medical events.

Neither the condition, hospitalization, prolonged hospitalization, nor surgery are reported as an AE in the following circumstances:

- Hospitalization or prolonged hospitalization for diagnostic or elective surgical procedures for a preexisting condition. Surgery should **not** be reported as an outcome of an AE if the purpose of the surgery was elective or diagnostic and the outcome was uneventful.
- Hospitalization or prolonged hospitalization for therapy of the target disease, unless it is a worsening or increase in frequency of hospital admissions as judged by the clinical investigator.
- An Emergency Room visit is not considered hospitalization.
- All AEs that do not meet any of the criteria for seriousness should be regarded as **non-serious AEs**
- **A pre-existing condition** is one that is present at the start of the study. A pre-existing condition should be recorded as an AE if the frequency, intensity, or the character of the condition worsens during the study period.
- At the end of the study, any new clinically significant findings/abnormalities that meet the definition of an AE must also be recorded and documented as an AE.

Detailed information about intensity, relationship to study drug, expectedness, serious criteria, follow-up and reporting of AEs and SAEs are provided in Section [12.2](#).

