12.4. Recording Adverse Events

Adverse events spontaneously reported by the patient/subject and/or in response to an open question from the study personnel or revealed by observation will be recorded during the study at the investigational site. Clinically significant changes in laboratory values, blood pressure, and pulse need not be reported as AEs. However, abnormal values that constitute an SAE or lead to discontinuation of administration of study drug must be reported and recorded as an AE.

Information about AEs and SAEs will be collected from the first administration of study drug through the follow up visit. The AE term should be reported in standard medical terminology when possible. For each AE, the investigator will evaluate and report the onset (date and time), resolution (date and time), intensity, causality, action taken, serious outcome (if applicable), and whether or not it caused the patient to discontinue the study.

It is important to distinguish between serious and severe AEs. Severity is a measure of intensity whereas seriousness is defined by the criteria under Section 12.2. An AE of severe intensity may not be considered serious.

Should a pregnancy occur in a subject or a male subject’s partner, it must be reported and recorded on SKLSI’s pregnancy form. Pregnancy in itself is not regarded as an AE unless there is a suspicion that an investigational product may have interfered with the effectiveness of a contraceptive medication.

The outcome of all pregnancies (spontaneous miscarriage, elective termination, normal birth or congenital abnormality) must be followed up and documented even if the patient was discontinued from the study.

All reports of congenital abnormalities/birth defects are SAEs. Spontaneous miscarriages should also be reported and handled as SAEs. Elective abortions without complications should not be handled as AEs.

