12.5.2. Serious Adverse Reporting

The Investigator or any other study center personnel's knowledge will notify any SAEs including fatal or life-threatening to SK Life Science, Inc. (SKLSI) and their designee IQVIA on an SAE report form, without regard to causality, within 24 hours after becoming aware of its occurrence.

If, during follow-up, any non-serious AE worsens and eventually meets the criteria for an SAE, that AE should be recorded as a new SAE.

The initial SAE report must be as complete as possible, including details of the current illness and SAE, and an assessment of the causal relationship between the event and the investigational product. Information not available at the time of the initial report (e.g., an end date for the AE, laboratory values received after the report, or hospital discharge summary) must be documented and an updated SAE report form should be forwarded to the Sponsor and their designee IQVIA within 24 hours of new/updated information. All follow-up information must be reported as soon as the relevant information is available. The notification of all SAE's should be directed to the following Sponsor representatives ([Table 12](#) and [Table 13](#)).

Table 12: Contact Information for IQVIA

Name	IQVIA
Email	[contact]
[contact]
[contact]

Table 13: Contact Information for Sponsor Medical Monitor

Name	[name]
Email	[contact]
[contact]

Table 14: Contact Information for PRA Principal Investigator

Name	[name], CPI
Email	[contact]
[contact]
[contact]

In addition, reporting of serious adverse events should follow the procedures outlined in [Table 15](#) based on the type of SAE.

Table 15: Serious Adverse Event Reporting Requirement

Type of SAE	Reporting Time Frame	Reporting Method	Contact Details
Rash with involvement of 1 other organ system or a suspected case of DRESS	Immediate	Email ^a	
Fatal or Life-threatening	Immediate	Email ^a	
All other SAEs	Within 24 hours of awareness	Email ^a	
Urgent safety concerns requiring a Medical Monitor	As needed	Telephone	

^aThe SAE report must be used for reporting

DRESS=Drug Reaction with Eosinophilia and Systemic Symptoms; SAE=serious adverse event; SKLSI=SK Life Science, Inc.;

At the time of the initial SAE report, the investigator should provide as much of the following information as possible:

- Study identifier;

- Study site;
- Subject number;
- A description of the event;
- Date of onset;
- Current Status;
- Whether study drug was discontinued;

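### Protocol 12.1.8.7 removes pregnancy complications and medically indicated terminations from AE and SAE reporting with no exception for seriousness, which conflicts with 12.2.1.2 and goes further than 12.4

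*Protocol*

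**What the plan says.** Four parts of the protocol bear on this.

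- **Section 12.1.8.7 (Pregnancy)** sets the exclusion: "Pregnancy complications and elective terminations for medical reasons should not be reported as an AE or SAE". The next two sentences are "All reports of congenital abnormalities/birth defects are SAEs" and "Spontaneous miscarriages should also be reported and handled as SAEs". The section also requires the pregnancy to be reported within 24 hours of its becoming known, followed to its outcome (including terminations and complications in mother or newborn), recorded on a Pregnancy Form, and assessed for a causal link to the study drug.
- **Section 12.2.1.2 (SAE definition)** covers "any untoward medical occurrence that at any dose" meets a listed criterion. The criteria include "Is life-threatening", an unplanned hospital stay of at least 24 hours, and "Is a congenital anomaly or birth defect". A separate list names circumstances that are not reported, such as elective or diagnostic surgery for a pre-existing condition. Pregnancy complications are not on it.
- **Section 12.4 (Recording Adverse Events)** has a narrower exclusion: "Elective abortions without complications should not be handled as AEs". It has none for pregnancy complications.
- **Section 12.5.2** requires SAEs to go to the sponsor and its designee "without regard to causality, within 24 hours after becoming aware of its occurrence". It also sets the IRB reporting times and makes the sponsor responsible for evaluating events for expedited reporting.

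The SAP has no rule for pregnancy events. SAP 6.1 lists AEs and SAEs as reported.

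**The concern.** The exclusion covers pregnancy complications as a class. An investigator with a seriously ill pregnant subject finds one section calling the event an SAE and another saying not to report it as an AE or SAE. The pregnancy section is the more specific of the two, so it is the one likely to be followed.

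What is at stake is how and when a serious event is handled. Section 12.1.8.7 wants the pregnancy followed because of possible exposure to the study drug, yet its exclusion takes the more serious maternal events off the fastest reporting route. The paragraph is also uneven within itself: a spontaneous miscarriage is always handled as an SAE, while a life-threatening complication of another kind is not.

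**Working it through.** No arithmetic applies, since the point concerns reporting rules. The check sets the sections side by side for each type of event in a trial subject.

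| Event in a subject | 12.1.8.7 | 12.2.1.2 | 12.4 | Result |
|---|---|---|---|---|
| Complication that is life-threatening or needs an unplanned stay of at least 24 hours | Neither AE nor SAE | SAE | Not excluded | Contradiction |
| Complication meeting no seriousness criterion | Neither AE nor SAE | Not an SAE | Not excluded | A carve-out from AE reporting; no serious-event rule is broken |
| Termination on medical grounds, with a complication | Neither AE nor SAE | SAE if the complication meets a criterion | Outside the exclusion | 12.1.8.7 is broader than 12.4 |
| Termination on medical grounds, no complication | Neither AE nor SAE | Not an SAE in itself | Excluded | Agree |
| Congenital anomaly or birth defect | SAE | SAE | SAE | Agree |
| Spontaneous miscarriage | SAE | No separate rule | SAE | Agree |

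Only the first and third rows conflict. For an event in either row, compare the two routes.

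1. **As an SAE.** It is reported to the sponsor and designee within 24 hours whatever the cause. It goes to the IRB within 3 working days, or within 24 hours if it is unexpected and fatal or life-threatening. The sponsor evaluates it for expedited reporting (all 12.5.2), and it appears in the SAP 6.1 listing.
2. **As a pregnancy outcome only.** The 24-hour clock in 12.1.8.7 starts from knowledge of the pregnancy. Neither 12.1.8.7 nor 12.4 sets a deadline for reporting a later outcome. The steps in item 1 depend on SAE status, so they need not happen.

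Two limits on reach follow from the text.

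- **Time.** AE collection ends at the follow-up visit (12.1.1, 12.4, 12.5.1), which is Day 69 ± 1 day, and SAP 6.1 ends the treatment-emergent period at Day 69. That is 69 − 1 = 68 days after the first dose. Later outcomes lie outside routine AE collection whatever this sentence says.
- **Population.** An inclusion criterion (number 8 in the synopsis, 10 in section 8.1) describes women of non-childbearing potential. Other text still provides for women of childbearing potential: the pregnancy-test footnote to Table 4, withdrawal on a positive test in 7.4.1, the hormonal-contraceptive exception in 9.2, and the contraception rules in 12.1.8.8. The exposed group is some unknown part of 24 subjects.

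**The case against.** The strongest reply is that nothing is lost from view. The pregnancy must be reported within 24 hours to the Medical Monitor, the sponsor and the safety designee, and SAE notices go to the sponsor's representatives and the same designee. Complications in mother and newborn must be followed, causality must be assessed for any outcome, and 12.4 requires outcome follow-up even after discontinuation. This stands. A reader might infer from the exclusion that a serious complication would go wholly unreported, and the documents do not support that. The reply does not supply the SAE classification, or a deadline for a complication that arises after the pregnancy has been reported.

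A reader might also infer that a termination because of a fetal anomaly would hide the anomaly. It would not. The sentence after the exclusion makes every reported anomaly an SAE, and 12.2.1.2 and 12.4 agree. The two sentences can be read together: the procedure is not an AE and the anomaly is an SAE. That matches 12.2.1.1, which says surgical procedures are not themselves AEs. At most, the text could say more plainly how the two apply together.

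Two smaller replies have some force. Section 12.4 does not state that complicated abortions are AEs; that is the natural implication of excluding only uncomplicated ones. And 12.2.1.1 defines an AE as occurring in a participating subject, so complications in a male subject's partner are outside this point. Neither reply removes the conflict with 12.2.1.2 over a serious complication in a subject.

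**Conclusion.** The inconsistency is real and narrow. As written, 12.1.8.7 conflicts with 12.2.1.2 for any pregnancy complication in a subject that meets a seriousness criterion, and it excludes more terminations than 12.4 does. The possible loss is SAE classification with its 24-hour report, the IRB SAE report, the evaluation for expedited reporting and, for events by Day 69, entry in the SAP 6.1 listing. The event itself would still be captured as a pregnancy outcome, and congenital anomalies keep their SAE status.

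The frequency will be low, and the documents give no rate from which to estimate it. The conclusion assumes that at least some women able to become pregnant may be enrolled, and that an investigator may follow the specific pregnancy section over the general definition. The PK endpoints, analysis populations and sample size are not affected.

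**What to change.** Reconcile the sentence in 12.1.8.7 with 12.2.1.2 and 12.4. One way is to limit the exclusion to uncomplicated elective terminations and to complications that meet no seriousness criterion. The section would then state that any event in a subject meeting a 12.2.1.2 criterion is reported as an SAE under 12.5.2 as well as on the Pregnancy Form. A few added words could confirm that, where a termination follows a fetal anomaly, the anomaly remains an SAE.

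The cost is rewriting one sentence in a protocol amendment. It adds no visit, sample or procedure and needs no change to the SAP.
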